# 7.1.1 Primary/Co-primary Efficacy Variable

The main co-primary estimands will be defined as follows:

Objective	Evaluate whether treatment with NT 201 is superior to treatment with placebo with respect to reducing sialorrhea
Population	Subjects treated
Variable(s)	uSFR and GICS, evaluated at 4 weeks after treatment in comparison to baseline
Handling of intercurrent events	To be defined during the BDRM
Population-level summary of the variable(s)	Difference in mean uSFR change from baseline to week 4 / mean GICS at week 4 between NT 201 and placebo

The main analytic approach or primary confirmatory analysis of the co-primary estimands will be a mixed model repeated measurement analysis (MMRM, 2-sided, significance level alpha=0.05) with comparison of least square means between NT 201 and placebo performed on the group of subjects within the FAS aged 6-17 years.

The dependent variables will be the change in uSFR from baseline (V2) to V3 (Week 4) ( $\Delta$ uSFR) and the carer's/parent's GICS at V3 (Week 4), respectively.

The independent variables are defined as treatment group, pooled investigation sites (see section 7.7.6) and age groups (6-9 years, 10-12 years and 13-17 years) as fixed factors, visit\*treatment as interaction term, and visit as repeated factor. To adjust for the baseline status, the MMRM of the uSFR change additionally includes the baseline score of the uSFR as covariate. Since no baseline assessment of the GICS is available, the baseline mTDS rated by the parent(s)/carer is used as covariate in the MMRM model for the GICS.

The following SAS code will be used:

```
proc mixed data = dataset;
  class treatment pooled_site age_group subject visit;
  model AuSFR (GICS) = treatment pooled_site age_group uSFR_baseline
        (mTDS) visit visit*treatment /solution ddfm=kr;
  repeated visit / subject = subject type = un grp = treatment
  LSMeans visit*treatment pooled_site age_group / pdiff CL alpha =
0.05;
run;
```

where:	treatment	= treatment group (NT 201 (6-17 years) and Placebo (6-17 years))
	pooled_site	= pooled investigation sites
	age_group	= age group (6-9 years, 10-12 years and 13-17 years)
	uSFR_baseline	= Value of uSFR at Visit 2 (Baseline)
	mTDS	= Value of mTDS at Visit 2 (Baseline)

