Only if both co-primary efficacy variables show a statistically significant difference compared to placebo the superiority of NT 201 over placebo will be considered to be proven. Therefore, no  $\alpha$ -adjustment for multiple testing is necessary.

Intercurrent events with potential bias on the co-primary endpoints will be identified prior to or during the BDRM. In case these events are judged as relevantly biasing the co-primary endpoints, conservative sensitivity analyses on the MMRM model will be specified during the BDRM.

In addition to the MMRM, an analysis of covariance (ANCOVA) model will be performed on the FAS (age 6-17 years) using observed cases as well as using the baseline observation carried forward approach (BOCF, no effect) for uSFR and imputing missing GICS entries as "no change". The ANCOVA models will be performed by use of the following SAS code:

```
proc mixed data = dataset;
  class treatment pooled_site age_group;
  model AuSFR (GICS) = treatment pooled_site age_group uSFR_baseline
        (mTDS)/solution ddfm=kr;
  LSMeans treatment pooled_site age_group / pdiff CL alpha = 0.05;
  where visit = V3;
run;
```

Furthermore, a non-parametric Wilcoxon rank-sum test will be performed as sensitivity analysis of the co-primary efficacy variables to investigate the impact of potential deviations from the assumption of normal distribution. The test will be performed for FAS (age 6-17 years) using observed cases as well as using BOCF for uSFR and "no change" for GICS. The Wilcoxon rank-sum test will be performed by use of the following SAS code:

```
proc npar1way data=dataset wilcoxon;
  class treatment;
  var ΔuSFR;
run;
```

For the GICS, a logistic regression will be performed as sensitivity analysis to the distribution assumption. The responder rate will be determined, i.e. all subjects with GICS entry of at least +1 (Minimally improved).

Treatment arm comparisons with respect to responders based on the GICS entries will be performed analogously to the primary efficacy analysis, but based on estimates of logistic regression models. The dependent variable of these models will be the response to treatment. Treatment group, pooled investigation site and age group will be included as factors into the models. Baseline adjustment will be done by including the baseline values of the mTDS as covariate. The following SAS code will be used for estimation:

```
proc logistic data=dataset desc order=formatted;

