#### 7.1.2 Secondary Efficacy Variables

The analyses of the secondary efficacy variables are also based on the subjects aged within the FAS 6–17 years.

The changes in uSFR from baseline (V2) to V4 and V5 (Week 8 and 12, respectively) and the GICS at V4 and V5 (Week 8 and 12, respectively) are analyzed analogously to the primary efficacy variables by means of a MMRM, ANCOVA and Wilcoxon rank-sum test with the analysis sets and methods to handle missing values as described in Section 7.1.1. Furthermore, the logistic regression will be performed for the GICS at V4 and V5.

Although these are "other" and not "secondary" efficacy variables, the uSFR change from baseline to V6 (Week 16) and the GICS at V6 will be included in the MMRM, ANCOVA and Wilcoxon rank-sum tables to give a complete picture over the main period. Furthermore, the logistic regression will be performed for the GICS at V6.

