# 7.7 Special Statistical/Analytical Issues

# 7.7.1 Discontinuations and Missing Data

Reasons for premature discontinuation by a subject will be summarized descriptively and listed. Where the discontinuation was due to an adverse event, this will be included in the listing of adverse events, and such events will be included as a category in the summary of adverse events.

The analysis of the primary and secondary efficacy variables will be performed using a MMRM as well as using an ANCOVA based on observed cases and an ANCOVA with missing values replaced by the baseline value or "no change" ('baseline observation carried forward approach'). By using all values of the dependent efficacy variable available in the timeframe underlying the MMRM, i.e. the main period, the MMRM reduces the influence of single missing values. The use of the ANCOVA model with missing values replaced by the baseline value is considered to be a conservative approach because if a comparable percentage of missing values is expected in both treatment groups (in the placebo group there may be more missing values due to lack of efficacy and in the verum group more due to adverse events) the replacement of missing values by the baseline value of the GICS – leads to a decrease in the difference of the observed treatment effects.

In general, values measured at the baseline injection visit (V2) will be used as study baseline value. If data is missing for this visit the last valid value before first injection will be used instead.

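### The SAS code for the Wilcoxon sensitivity test omits the visit restriction and the GICS variable that the SAP's own text requires

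*SAP*

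**What the plan says.** SAP 7.1.1 makes the MMRM the confirmatory analysis of the change in uSFR to Week 4 (V3) and of GICS at Week 4. It then says that "a non-parametric Wilcoxon rank-sum test will be performed as sensitivity analysis of the co-primary efficacy variables", to be run on observed cases and again with missing values set to baseline (uSFR) or to no change (GICS). The implementation is fixed: "The Wilcoxon rank-sum test will be performed by use of the following SAS code". The block opens with "proc npar1way data=dataset wilcoxon", followed by a CLASS statement for treatment and a VAR statement naming the uSFR change. It has no WHERE or BY statement.

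The ANCOVA block just above and the logistic block just below each contain "where visit = V3". Every block reads a data set given the same name. The MMRM block uses it with "repeated visit / subject = subject type = un grp = treatment", so there it holds several rows per child.

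SAP 7.7.1 describes the MMRM data: "By using all values of the dependent efficacy variable available in the timeframe underlying the MMRM, i.e. the main period". SAP 7.1.2 carries the Wilcoxon test to Weeks 8 and 12, and says that the Week 16 results "will be included in the MMRM, ANCOVA and Wilcoxon rank-sum tables to give a complete picture over the main period".

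**The concern.** The rank-sum test assumes one independent value per child. Without a visit restriction, the code ranks all main-period rows together and counts each child up to four times. The result is no longer a test of the Week 4 endpoint. Because rows from one child are likely to be positively correlated, the test also uses too small a variance. The same code applied under 7.1.2 would print one identical pooled p-value for Weeks 4, 8, 12 and 16.

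The VAR line leaves one of the two co-primary variables without code for this check, whereas the MMRM and ANCOVA blocks show GICS in parentheses as the alternative outcome.

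At stake is the plan's named check on whether the co-primary results depend on normality. SAP section 2 sets itself the aim of being precise enough to guide programming, and this block falls short of that aim.

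**Working it through.** **1. The code blocks of SAP 7.1.1 side by side**

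| Block | Handling of visit | Outcomes named |
|---|---|---|
| MMRM | model term and repeated factor | uSFR change (GICS) |
| ANCOVA | restricted to V3 | uSFR change (GICS) |
| Wilcoxon | none | uSFR change only |
| Logistic | restricted to V3 | GICS response |

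Of the three single-visit analyses, only the Wilcoxon lacks the filter.

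**2. Group sizes**

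SAP section 4 gives 146 NT 201 and 73 placebo children. Section 4.2 claims 95% power for a difference of 1.0 with SD 1.93 at two-sided 5%. Check: the standard error is 1.93 × sqrt(1/73 + 1/146) = 0.277, so 1.0/0.277 = 3.61, and Phi(3.61 − 1.96) = 95.1%. A noncentral t on 217 df gives 94.9%. The stated figure reproduces, and these group sizes are used below.

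Four visits per child would give 4 × 219 = 876 rows, against 219 rows at Week 4 alone.

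**3. Error rate if the code is run literally**

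Assumptions: no treatment effect at any visit, k complete rows per child, and equal correlation rho between visits. The documents do not give rho.

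The true variance of the rank-sum statistic is about 1 + (k − 1) × rho times the variance that the test assumes. The actual two-sided size at nominal 5% is therefore

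size = 2 × (1 − Phi(1.96 / sqrt(1 + (k − 1) × rho))).

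For k = 4 and rho = 0.5: sqrt(2.5) = 1.58, 1.96/1.58 = 1.24, size = 21.5%.

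| rho | k = 4 (Weeks 4, 8, 12, 16) | k = 3 (Weeks 4, 8, 12) |
|---|---|---|
| 0.1 | 8.6% | 7.4% |
| 0.3 | 15.5% | 12.1% |
| 0.5 | 21.5% | 16.6% |
| 0.7 | 26.6% | 20.6% |
| 0.9 | 30.8% | 24.2% |

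For k = 4 and rho 0.3 to 0.7, the standard error is understated by a factor of sqrt(1.9) = 1.38 to sqrt(3.1) = 1.76.

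**4. Simulation check**

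Each scenario used 6,000 simulated trials of 146 v 73 children under no effect, with a tie-corrected rank-sum test and continuity correction.

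- Continuous outcome, four visits, rho 0, 0.3, 0.5, 0.7: 5.2%, 14.7%, 21.6%, 26.1%.
- Seven-point outcome resembling GICS, four visits, rho 0.3, 0.5, 0.7: 14.9%, 20.4%, 25.9%.
- Correlation decaying with distance between visits (AR(1)), four visits, adjacent-visit rho 0.5, 0.7, 0.8: 16.8%, 23.1%, 26.3%.
- Three visits only, rho 0.3, 0.5, 0.7: 12.1%, 17.0%, 20.5%.
- Restricted to Week 4: 4.5–5.6% across all scenarios, which is the nominal level.

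**The case against.** The strongest reply is that the code is schematic. The MMRM and ANCOVA blocks write two outcomes in one MODEL line, which is shorthand and not runnable SAS. The data set name must be a placeholder, because the same code has to serve observed and imputed data and two analysis sets. The SAP also attaches the symbol for the uSFR change to the change from baseline to Week 4. The text calls the Wilcoxon a check on the Week 4 co-primaries and lists the later visits separately, which makes sense only visit by visit. A programmer would probably notice 876 records for 219 children.

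Much of this stands. A reader might infer that the SAP plans to pool visits. It does not: the text rules that out, and what remains is a conflict between code and text.

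The definition of the symbol does not remove the conflict. The MMRM block models the same symbol across visits, and the ANCOVA block still needs a V3 filter on it. If the code is only a sketch, it is one in which the authors wrote the filter twice and left it out once, while stating that this code will be used.

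A reader might also infer that the check would support the main result almost regardless of the Week 4 data. The figures do not support that: with no effect and correlation 0.3–0.7, the pooled test still fails to reject in about 73–85% of trials. Nor would a pooled p-value always be too small when there is a real effect. Protocol 6.2 expects the toxin effect to decay after 8–12 weeks, so adding later visits could dilute a Week 4 difference.

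**Conclusion.** The point holds as a disagreement between code and text in a sensitivity analysis. The Wilcoxon block lacks the visit restriction of its neighbours and omits GICS. Taken literally, it does not test Week 4 and is anticonservative under a null of no effect at any visit.

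The size is about 15–27% instead of 5% for an assumed within-child correlation of 0.3–0.7 with four visits. It is about 9–31% for correlations of 0.1–0.9, and about 12–21% for 0.3–0.7 if only Weeks 4, 8 and 12 are stacked. These figures depend on the assumed correlation and are not properties stated in the plan. Nothing in the documents shows that visits were pooled in practice.

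A reader might go further and doubt the confirmatory result. The documents do not support that. Superiority rests on the two MMRM tests alone, and SAP 7.7.4 makes all other tests descriptive. For GICS, the logistic model restricted to Week 4 gives a second check on the distributional assumption. This is a minor correction.

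**What to change.** In the NPAR1WAY block of SAP 7.1.1, add `where visit = V3;` for the co-primary check. Alternatively, sort the data by visit and add `by visit;`, which also covers Weeks 8, 12 and 16 under 7.1.2. Change the VAR line to show both outcomes in the notation of the other blocks, `var ΔuSFR (GICS);`.

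The cost is one or two lines of SAP text. The intended analysis does not change, and no additional data are needed.

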#### 7.1.2 Secondary Efficacy Variables

The analyses of the secondary efficacy variables are also based on the subjects aged within the FAS 6–17 years.

The changes in uSFR from baseline (V2) to V4 and V5 (Week 8 and 12, respectively) and the GICS at V4 and V5 (Week 8 and 12, respectively) are analyzed analogously to the primary efficacy variables by means of a MMRM, ANCOVA and Wilcoxon rank-sum test with the analysis sets and methods to handle missing values as described in Section 7.1.1. Furthermore, the logistic regression will be performed for the GICS at V4 and V5.

Although these are "other" and not "secondary" efficacy variables, the uSFR change from baseline to V6 (Week 16) and the GICS at V6 will be included in the MMRM, ANCOVA and Wilcoxon rank-sum tables to give a complete picture over the main period. Furthermore, the logistic regression will be performed for the GICS at V6.

# 7.2 Pharmacodynamic Variables

Not applicable.

# 7.3 Pharmacokinetic Variables

Not applicable.

CONFIDENTIAL Template: tem-sap-v4.0-20151126 File name: MRZ60201\_3091\_1-sap-final v1.0-2019-06-21.docx Page 25 of 46

# 7.4 Pharmacogenetic Variables

Not applicable.

# 7.5 Safety Variables

The safety variables will be analyzed for the SES of the MP or OLEX by using descriptive summary statistics, frequency tables, and shift tables where appropriate.

All analyses will be performed by age groups and treatment and additionally for the group of subjects of all ages (2-17) who received NT 201 in the respective treatment period (main or extension period), i.e. all analyses of the MP will be stratified by "Placebo (6-17 years)", "NT 201 (6-17 years)", "NT 201 (2-5 years)", "Total NT 201 (2-17 years)". For the OLEX, two sets of tables will be produced: one "respective of main period treatment" showing "NT 201 (MP=Placebo, 6-17 years)", "NT 201 (MP=NT 201, 6-17 years)", "NT 201 (MP=NT 201, 2-5 years") and another set "irrespective of main period treatment" showing "NT 201 (6-17 years)", "NT 201 (2-5 years)" and "NT 201 (2-17 years)". OLEX tables for non-serious TEAEs with incidence  $\geq$  5%, C-SSRS and Botulinum toxin antibody results will only be presented irrespective of main period treatment.

For all OLEX tables which are stratified by visit/cycle, only subjects with injection in the respective cycle are included. For End of Study all subjects from SES (OLEX) will be included and the results from V18 will be used. Visit "Cycle 4 Week 16" will not be analyzed.

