As no substance has yet received marketing approval for the treatment of chronic troublesome sialorrhea for minors in the EU, and to date no appropriately powered pivotal study data on *Botulinum* toxin in this indication are available, therefore placebo treatment in about 33% of all enrolled and randomized subjects (age 6–17 years) for one single injection cycle during the main period out of a total of four injection cycles is justified. All children age 2–5 years will receive NT 201 in the main period. However, it was also considered to be important not to withhold treatment from subjects needing it in this burdensome indication. Therefore, the placebo group in the main period was kept small, and the extension period (required by the need for long-term safety data) was designed without placebo treatment. All subjects will receive active treatment during the extension period. All subjects are expected to benefit from treatment with NT 201 (subjects in the placebo group three times, subjects in the active treatment group four times).

Following discussions with the relevant regulatory authorities, it was considered necessary to follow at least 100 children treated with clinically relevant doses of NT 201 continuously for one year. At least 50 of these patients must have received the high dose (at least 2 U/kg body weight) consistently for one year (series of four injections). The safety database requirement in children for cumulative exposure at six months is also at least 100 subjects treated consistently with clinically relevant dosages for two injections.

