## 9.1.2.3 Antibodies against Botulinum toxin

To detect antibodies against *Botulinum* toxin in study subjects the fluorescence immunoassay [FIA] and the hemidiaphragm assay [HDA] will be used.

Blood will be sampled for analysis of antibodies against BoNT for subjects with  $\geq$ 30 kg BW. For children with <30 kg BW no blood samples for analysis of antibodies against BoNT will be taken. Blood amounts will be taken according to the weight group of the subject in context of all blood withdrawals during the study (Section 9.1.7). For subjects with  $\geq$ 30 kg BW first blood samples are taken at baseline (V2). Subsequent antibody tests after repeated IP exposure will be performed for subjects with  $\geq$ 30 kg BW only at the end-of-study visit (V18; alternatively, if preferred, at V17).

The serum amount necessary for FIA-AB is 1.5 mL and 4.5 mL for HDA. To yield the required serum amount the estimated blood amount is 4.9 mL for FIA-AB and 15 mL (2x7.5 mL) for HDA. Sample work-up at the study site includes preparation of serum by centrifugation at room temperature and transfer into provided tubes. Serum samples should preferably be stored at -20°C ( $\pm$ 5°C) but must be within a range of -5°C to -90°C until frozen shipment to the analyzing laboratory.
Blood samples will be screened using the FIA-AB that detects antibodies against BoNT A in human serum. FIA-AB detects binding to specific BoNT epitopes and allows the identification of sera that react with the toxin, but the FIA-AB is not capable to discriminate between neutralizing and non-neutralizing antibodies [Goschel 1997].

Samples that are positive in the FIA-AB will be tested using the validated mouse ex vivo HDA. The HDA is the most sensitive functional assay (sensitivity <0.5 mU/mL) currently available [Sesardic 2004]. To spare animals, the assay is performed only if the FIA-AB is positive.

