#### Antibodies against BoNT-A

Occurrence of antibodies against BoNT-A in subjects with  $\geq 30$  kg BW will be analyzed descriptively (frequency tables by category and shift tables from baseline (V2) to end-of-study visit V18) and screened for individual notable values and/or changes. In case blood sample is taken at V17 instead of V18 these values are used for analyses.

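### The extension-period antibody tables pool children planned for three and for four NT 201 injections, so they give no antibody rate for the four-injection course

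*SAP*

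**What the plan says.** - **Who is sampled and when.** Protocol 9.1.2.3 restricts antibody sampling to children of at least 30 kg: "For children with <30 kg BW no blood samples for analysis of antibodies against BoNT will be taken". One sample is taken at V2, before any NT 201. One is taken after repeated exposure, at V18 or, if preferred, V17.
- **Planned analysis.** The antibody paragraph of SAP 7.5 plans "frequency tables by category and shift tables from baseline (V2) to end-of-study visit V18", plus screening for notable individual results. A V17 result stands in for V18 where that visit was used.
- **Which tables.** SAP 7.5 sets two families of extension-period safety tables, one by main-period arm and one pooled, and then makes an exception: "C-SSRS and Botulinum toxin antibody results will only be presented irrespective of main period treatment". It gives no reason, and neither does SAP section 8.
- **Who enters the end-of-study table.** "For End of Study all subjects from SES (OLEX) will be included and the results from V18 will be used". Under Protocol 12.2 and SAP section 5, that set needs only one extension injection.
- **Planned exposure.** Protocol 6.2 gives the planned number of NT 201 treatments as "subjects in the placebo group three times, subjects in the active treatment group four times".

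**The concern.** Antibodies are tested to see what repeated exposure does, and the two main-period arms differ by design in the number of NT 201 injections before the only post-baseline sample. Protocol 6.2 also records that regulators wanted at least 50 children followed through a series of four injections at the higher dose level. The planned tables report one antibody rate for a mixture of exposures and none for children who had the full course. If antibody formation rises with each injection, the mixed figure is too low for the four-injection course, and the table gives no sign of it. This is the trial's only planned immunogenicity measurement, and it covers only the heavier children.

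**Working it through.** **The plan's own figure.** The documents give no antibody figure. The relevant stated number is the sample size, because it sets the mix of arms. With a difference of 1.0, SD 1.93, two-sided alpha 0.05, 95% power and 2:1 allocation:

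n(placebo) = (1 + 1/2) × (1.960 + 1.645)² × 1.93² / 1.0² = 72.6, so 73; total 3 × 73 = 219.

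This reproduces 146 + 73 (power 0.951 by the normal formula, 0.949 by the noncentral t).

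**Planned exposure at V18.** Sampled children fall in the fixed 75 U class. If they stay in it without dose reduction, the cumulative dose is 4 × 75 = 300 U against 3 × 75 = 225 U. The expected share with three injections is 73/219 = 1/3. That share is expected, not fixed, in the sampled children, because Protocol 8.2.1 describes randomization lists by age group and not by weight. The set also admits early leavers, so the count can run from 1 (placebo arm, one extension injection) to 4.

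**Size of the understatement, completers aged 6–17.** Pooled rate = (1/3) × r3 + (2/3) × r4, where r3 and r4 are the rates after three and four injections.

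| Assumed rates | Pooled | Pooled / r4 | Understatement of r4 |
|---|---|---|---|
| Proportional, r3 : r4 = 3 : 4 | 1 + 2.667 = 3.667 units (r4 = 4) | 0.917 | 8% |
| 1% and 3% | 0.33 + 2.00 = 2.3% | 0.78 | 22% |
| 2% and 10% | 0.67 + 6.67 = 7.3% | 0.73 | 27% |
| 0 and r4 (all after the fourth injection) | 0.667 × r4 | 0.667 | 33%, the ceiling |

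Every rate here is an assumption.

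**What stays visible.** The comparison of V2 with V18 survives pooling. At assumed rates of 1% and 3%, the chance of at least one positive at V18 is 1 − 0.99^n3 × 0.97^n4. If 30% to 100% of children are sampled and none drop out, this is 79% to 99%.

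**What a split could show.** The share of at least 30 kg and the dropout rate are not stated, so both are varied. Power is exact, for a two-sided Fisher test at 0.05. The upper bound is the one-sided 95% limit 1 − 0.05^(1/n) when no positive is seen.

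| Share sampled | n, three v four injections | Power, 1% v 3% | Power, 2% v 10% | 2% v 10% with 30% dropout | Upper bounds if no positives |
|---|---|---|---|---|---|
| 30% | 22 v 44 | under 1% | 5% | 1% | 12.7% / 6.6% |
| 50% | 36 v 73 | under 1% | 16% | 8% | 8.0% / 4.0% |
| 70% | 51 v 102 | under 1% | 34% | 22% | 5.7% / 2.9% |
| 100% | 73 v 146 | 2% | 57% | 34% | 4.0% / 2.0% |

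Except in the dropout column, no dropout is assumed. A split would therefore describe each exposure level but could not reliably show or exclude a trend at low rates.

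**The case against.** The case for leaving the SAP alone has several sound parts.

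- **Emergence is tabulated.** A reader might infer that pooling hides any rise of antibodies with exposure. It does not: the "shift tables from baseline (V2) to end-of-study visit V18" compare no NT 201 in this trial with repeated NT 201. Only the contrast between exposure levels is lost.
- **Individual results remain.** A reader might also infer that the SAP bars any view by arm. The exception governs summary tables. SAP section 5 has the listings carry and sort by treatment group, so a few positives could be traced by hand. The demographic tables in SAP 7.6, shown by main-period arm with a class of at least 30 kg at baseline, should give rough denominators. The table shells in SAP Appendix 1 are not available here.
- **The arm contrast is not a clean test of injection number.** At V18 the NT 201 arm is about 64 weeks from its first NT 201 and the placebo arm about 64 − 16 = 48 weeks. The extension set is selected after randomization. Toxin given more than a year before screening is not excluded. A grouping by injections actually received is not randomized at all.
- **No commitment is broken.** The protocol plans a descriptive antibody analysis with no split by arm, and results outside the co-primary tests are descriptive.

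All of this stands, and it limits the point. None of it supplies a reason for the exception or yields a tabulated rate for the four-injection course.

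**Conclusion.** The point holds as a minor weakness of presentation. No planned summary table separates on-treatment antibody results by main-period arm or by number of NT 201 injections, so the trial would report no antibody rate for its own full course. In completers aged 6–17 the understatement runs from about 8% (rates proportional to injections) to at most one third. It is tempting to quote one third as the size of the problem, but that requires no new antibodies at all after three injections, which nothing in the documents supports. The figures rest on the planned 2:1 mix carrying over to children of at least 30 kg, and on assumed rates. The primary analysis, error rate, sample size and safety rules are unaffected.

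**What to change.** Remove antibody results from the exception in SAP 7.5. Present the frequency table and the V2-to-V18 shift table by main-period arm as well as pooled, using actual main-period treatment as SAP section 5 already specifies for safety data. Add a breakdown by number of NT 201 injections received before the sample, labelled descriptive and non-randomized, so that early leavers are placed correctly. A footnote should say that the arms also differ in time since first NT 201, and that small cells do not support a conclusion of no difference.

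The column headings already exist for the other extension safety tables and no new data are needed. The cost is the additional descriptive tables, with small cells and wide intervals, recorded as an SAP amendment or as an additional descriptive analysis in the study report.
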